4.1. Inclusion Criteria

- Male or Female Miner employed at the Peabody El Segundo mine in McKinley County, NM (i.e., intervention mine) or the Peabody Caballo and Rawhide mines at Campbell County, WY (i.e., control mine).
- ≥ 18 years of age.
- Willing and able to provide and sign Informed Consent Form.
- Willing and able to comply with study procedures.

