This is a single site study (i.e., at UNM HSC), with recruitment at two mine sites. This does not qualify as multi-site search. This study will take place and recruit participants at the (1) Peabody El Segundo Mine in McKinley County, NM at the edge of Navajo Nation (i.e., intervention mine), and the (2) Peabody Caballo and Rawhide mines at Campbell County, WY (i.e., control mine). Laboratory diagnostic testing will be conducted at TriCore Reference Laboratories. Since the diagnostic test is qualitative, we will also quantify viral load (\log_{10} copies/mL) from nasal (self-collected) and NP (collected by healthcare personnel) swab specimens using RT-qPCR established in the research laboratory of [name] at the Center of Global Health in the University of New Mexico’s Department of Internal Medicine. Data storage and analysis will be conducted at the University of New Mexico Health Sciences Center. The PI will have regular communication with the locations to confirm all research staff are competent, properly trained; they will have the most current version of the protocol, consent documents, and HIPAA authorization; any modifications will be communicated to sites and implemented only after IRB approval; they will safeguard all research data; any non-compliance with the study protocol or applicable requirements will be reported immediately to the PI; all adverse events, interim results and study closure determinations will be communicated via email and/or teleconference between the PI and study staff.

12. Study Procedures

During the baseline study visit, former miners and never-miners will complete a comprehensive baseline survey. Additional study procedures are outlined below

Overview of study procedures		
Measurement	Intervention mine, NM, n=less than 250	Control mine, WY, n=less than 350
Baseline survey: Demographics (age or DOB, gender or sex, race and ethnicity, education, household income, insurance, height, weight, Mailing residential address and if PO Box, physical mailing address, phone number, medical history including hypertension, diabetes, COPD, asthma, pneumoconiosis, immunocompromised state, cardiovascular disease, smoking, environmental tobacco smoke exposure, home access to running water, use of household wood or coal smoke, d tobacco, , current medications, history of prior COVID hospitalization, shared transportation	At the time of study enrollment, using paper and/or REDCap	

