Predictor and Outcome variables: The predictor variable is the mine status. The primary outcome is any new seropositivity for SARS-CoV-2 IgM or IgG at 3, 6, or 12 months relative to baseline. The test allows for the qualitative detection of IgG and/or IgM antibodies (separately) against SARS-CoV-2, indicating recent (IgM: 3-5 days) or prior infection (currently unknown). The tests have positive percent agreements of 97% and 87% and negative percent agreements of 98% and 99% for IgG and IgM, respectively, compared to oropharyngeal swab RT-PCR. We will also study the presence of symptoms or fever, irrespective of infection status, as an alternative study outcome for hypothesis 3A. Costs of the test-based surveillance program, employee absenteeism patterns, and mine coal production will contribute towards defining the outcome variables for hypothesis 3B. At a minimum, a valuable outcome is to determine surveillance program costs, which have not been previously established for this rural industry setting, organization size, or proposed surveillance frequency. Additionally, variance in outcome measures—defined as employee days lost due to incident infection, mine productivity, and reduction in worksite infection rate—across the two sites will be used to estimate the cost-effectiveness of the intervention. Database management and timeline are similar to that for Aim 1.

PROTOCOL TITLE: Keeping rural minority ‘essential’ workplaces open safely during the COVID-19 pandemic: The role of frequent point-of-care molecular workplace surveillance for miners

Covariates: Baseline seropositivity, vaccination status, other host susceptibility and vulnerability factors outlined in Table 1, and daily community prevalence and incidence, will be studied as covariates in multivariable models (35).

Statistical analysis: Chi-square tests will examine whether relative frequencies of incident seropositive miners are the same at 3-months, 6-months, and 12-months for the two mine types, using $\alpha=0.025$ to account for the two tests. Generalized linear models for repeated binary outcomes will be used to assess how covariates are associated with seropositive status over time.

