Power calculation: Based on representative seroprevalence/molecular prevalence rates for similar communities (36), we anticipate a 10% baseline seropositivity with incident seropositivity at 6 months at 5% for the intervention mine and a baseline seropositivity of 5% in the control mine. We anticipate similar power calculations to apply up to 12 months. We explored a range of control miner incident seroprevalence values that would have 80% power when comparing frequencies at the two mines using chi-square tests. We expect 80% power if incident seropositivity at the control mine is $\geq 9\%$ ($\alpha=0.025$).

13.4. Specific Aim 4:

Statistical analysis: Chi-square and logistic regression analyses will be used to explore how miner characteristics are associated with baseline seropositivity. Generalized linear models for repeated binary outcomes will be used to assess how predictor variables (noted in Table 7) and covariates (as noted in Aim 3) are associated with incident seropositivity at 3, 6, & approximately 12 months. Both analysis strategies will include mine type as a covariate and will add predictor and outcome variables noted in Table 7.

Table 7: List of predictor and outcome variables for Aim 4

Predictor and outcome variables	Time of measurement	Procedure for ascertainment
Frequency of cloth face-covering use outside the mine	On the day of the screening test; Mean summary variable over the one week before the test	Self-report, via the app, every work shift
Occupational dust exposure intensity	On the day of the screening test; Mean summary variable over the one week before the test	Mine safety team, via job-exposure matrix, every shift
Presence of lung disease	Baseline	Baseline survey
Race/ethnicity status	Baseline (at study enrollment)	Self-report via questionnaire
Facilitators and barriers	Between 6 and 12 months	Self-report via questionnaire
Test and vaccine uptake	Between 6 and 12 months	Self-report via questionnaire

Power calculation: We assessed power, using simulation for incident seropositivity at 6 months with mine type as covariate and a predictor miner variable, such as high dust exposure. We anticipate similar power calculations up to 12 months. We assumed the miner variable, present in 1/3 sample, will increase the probability of incident seropositivity by 0.10. For a logistic regression analysis and this setup, power is $>96\%$.

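### Hypothesis 3A is tested as if miners were independent, so alpha 0.025 holds only if mines do not differ, and the 80% power figure needs restating

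*Combined protocol and SAP*

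**What the plan says.** Sections 4.1, 5, 8, 11 and 20 name three mines. El Segundo in New Mexico receives frequent testing. The comparator is "the Peabody Caballo and Rawhide mines at Campbell County, WY (i.e., control mine"). Section 11 describes a study "with recruitment at two mine sites".

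In section 13.3 the primary outcome is "any new seropositivity for SARS-CoV-2 IgM or IgG at 3, 6, or 12 months relative to baseline", and "The predictor variable is the mine status". The test is given as: "Chi-square tests will examine whether relative frequencies of incident seropositive miners are the same at 3-months, 6-months, and 12-months for the two mine types". Each test has a level of 0.025, which the section describes as an allowance for two tests. The power paragraph takes 5% incident seropositivity at 6 months in the intervention mine and continues: "We expect 80% power if incident seropositivity at the control mine is" at least 9%, at alpha 0.025.

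Section 13.3 also plans generalized linear models for repeated binary outcomes, with baseline seropositivity, vaccination, host factors and community rates as covariates. Section 13.4 adds mine type as a covariate. No section gives an ICC, a design effect, a mine-level variance term, or separate reporting of Caballo and Rawhide.

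**The concern.** The chi-square counts miners as independent observations. Section 2 says that infection is often passed on at work, and the intervention is meant to interrupt that spread. If so, co-workers' outcomes are correlated, and mines will differ by the chance course of outbreaks even when testing does nothing. With one intervention mine, such a difference cannot be separated from an intervention effect, and a miner-level standard error leaves it out.

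Two things are at stake. The error rate attached to 3A is not assured by the design. And section 3.3 intends 3A to establish effectiveness and support a prevention strategy, so a chi-square that reacts to an ordinary outbreak difference could be reported as that evidence.

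**Working it through.** **Inputs from the documents.** Fewer than 250 intervention and 350 control miners (section 5). Baseline seropositivity 10% and 5%, intervention incidence 5%, control incidence 9%, alpha 0.025 per test (section 13.3). Miners at risk of new seropositivity are therefore at most 250 × 0.90 = 225 and 350 × 0.95 ≈ 332.

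**Assumed, because the documents do not say.** The ICC (0 to 0.02), and an equal split of the control miners between Caballo and Rawhide.

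**Step 1: the plan's own power, under independence.** Power = Φ[(|p2 − p1| − z·s0)/s1], with z = 2.241 (two-sided 0.025), s0 the pooled and s1 the unpooled standard error.
- 250 and 350 miners: pooled rate (12.5 + 31.5)/600 = 0.0733, s0 = 0.02159, s1 = 0.02059. Φ[(0.04 − 0.04838)/0.02059] = Φ(−0.407) = 34%.
- 225 and 332 miners: s0 = 0.02258, s1 = 0.02140. Φ[(0.04 − 0.05062)/0.02140] = Φ(−0.496) = 31%.

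The stated 80% is not reproduced. On the same formula, 80% needs control incidence of about 12% to 13%.

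**Step 2: type I error with mine-level variation.** The true variance of the difference exceeds the independence variance by the factor

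V = {[1 + (n1 − 1)ρ]/n1 + [1 + (nc/2 − 1)ρ]/nc} / (1/n1 + 1/nc),

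where ρ is the ICC, n1 = 225 and nc = 332. True two-sided error ≈ 2[1 − Φ(2.241/√V)]. At ρ = 0.01: V = (3.24/225 + 2.65/332)/(1/225 + 1/332) = 0.02238/0.00746 = 3.00, and 2[1 − Φ(1.294)] = 19.6%.

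This was checked by 400,000 simulated studies per setting: beta-distributed mine rates with the same mean in all three mines, then the pooled chi-square without continuity correction. The between-mine SD is √[ρp(1 − p)]. Paired entries are for mean incidence 5% / 9%.

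| ICC | Between-mine SD (points) | V | Formula, two-sided | Simulated, two-sided | Simulated, falsely favouring testing |
|---|---|---|---|---|---|
| 0 | 0 | 1.00 | 2.5% | 2.7 / 2.5% | 1.0 / 1.2% |
| 0.001 | 0.7 / 0.9 | 1.20 | 4.1% | 4.3 / 4.1% | 1.7 / 1.9% |
| 0.002 | 1.0 / 1.3 | 1.40 | 5.8% | 6.0 / 5.8% | 2.5 / 2.7% |
| 0.005 | 1.5 / 2.0 | 2.00 | 11.3% | 11.4 / 11.2% | 5.0 / 5.4% |
| 0.01 | 2.2 / 2.9 | 3.00 | 19.6% | 19.2 / 19.5% | 8.9 / 9.6% |
| 0.02 | 3.1 / 4.0 | 5.00 | 31.6% | 31.0 / 31.5% | 15.5 / 16.0% |

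The nominal rate for the last column is 0.025/2 = 1.25%. If the two Wyoming mines behaved as a single cluster, the two-sided error at ICC 0.01 would be about 24%.

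**Step 3: is the ICC range plausible?** The only hint in the documents is the anticipated baseline of 10% and 5%. The mean is 0.075, and p(1 − p) = 0.0694. The variance of the two values is 0.000625 (divisor 2) or 0.00125 (divisor 1), so the implied ICC is 0.009 to 0.018. This is one pair of anticipated prevalences, not incidences, so it illustrates and does not estimate.

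**Step 4: power once mines may differ.** For 5% versus 9% with 250 and 350 miners, treat the ICC as known and multiply each mine type's binomial variance by 1 + 249ρ (intervention) or 1 + 174ρ (control). At ρ = 0.01 the standard error is √(0.0475 × 3.49/250 + 0.0819 × 2.74/350) = 0.0361, and power is Φ(0.04/0.0361 − 2.241) ≈ 13%. At 0.001, 0.005 and 0.02 it is about 32%, 19% and 8%. This version uses the unpooled standard error, so its value at ICC 0 is 38%, not the 34% of step 1.

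**The case against.** The strongest reply is that the size of the problem rests on an ICC that no document supplies. That stands: at 0.001 the two-sided error is only about 4%. A reader might infer that ordinary mine-to-mine variation will often be declared an intervention effect. The documents do not support that prediction. Hypothesis 3A is also directional, and about half of the excess rejections favour the control mines. What can be said is that alpha is not assured, and how far it moves over a stated range.

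Second, the plan adjusts for baseline serostatus, vaccination and community rates in multivariable models, and section 1 calls the study a proof of principle. This bears on known differences between the mines. It does not change the chi-square or the power figure, neither of which uses those covariates. Mine type as a covariate in section 13.4 separates two types, not three mines, and adds no between-mine variance.

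Third, a reader might infer that the shared control label means mine identity is thrown away. No section says so, and both Wyoming mines are named throughout. The gap is that no analysis by mine is planned.

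Fourth, splitting the control mines does not rescue the test. One mine against two leaves 1 degree of freedom, with a critical value of 25.5 at two-sided 0.025. Caballo and Rawhide share county, state and operator, so their difference cannot show how New Mexico and Wyoming differ. This objection stands and shapes the fix.

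**Conclusion.** The concern holds in this form: the 3A chi-square is a miner-level test of an intervention assigned to one mine, and alpha 0.025 is valid only with no between-mine variation. Over an assumed ICC of 0.001 to 0.02, true two-sided error is about 4% to 31%, and the chance of a false benefit is about 2% to 16% against 1.25%. These figures rest on the maximum planned numbers, an equal Wyoming split, 5% to 9% incidence in all mines, and a single test at 0.025. How that alpha is shared among time points is a separate matter.

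A reader might conclude that the 80% power is right so long as mines do not differ. It is not: independence already gives only about 31% to 34%, so attaching that condition to the 80% would leave a false statement in section 13.3. Mine-level variation lowers power further, but it is not the first cause of the shortfall.

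**What to change.** In section 13.3:

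1. Keep a mine identifier in the analysis dataset. Report incident seropositivity with confidence intervals separately for El Segundo, Caballo and Rawhide. Show the Caballo–Rawhide difference as descriptive context only, not as a decision rule.
2. As a sensitivity analysis, show the New Mexico versus Wyoming difference with its standard error multiplied by √V over a stated ICC range, for example 0 to 0.02. Do not claim effectiveness from the unadjusted chi-square alone.
3. State that alpha 0.025 assumes no between-mine variation, and that 3A is a non-randomised comparison with one intervention mine.
4. Replace the 80% statement. Under independence, 5% versus 9% has about 31% to 34% power, and 80% needs control incidence of about 12% to 13%. Add that power is lower once mine-level variation is allowed for.

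The cost is SAP wording, one variable and a short sensitivity table, with no extra miners or sites. The downside is a more cautious conclusion and a less favourable power figure.

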4.2. Exclusion Criteria

- Unable or unwilling to provide and sign Informed Consent Form
- < 18 years of age.

PROTOCOL TITLE: Keeping rural minority ‘essential’ workplaces open safely during the COVID-19 pandemic: The role of frequent point-of-care molecular workplace surveillance for miners

We will not recruit or enroll pregnant women, incarcerated individuals, minors, or adults unable to consent.

5. Number of Subjects

Less than 600 subjects will be recruited at all mine sites in this longitudinal study. Of these, less than 250 miners will be recruited from the Peabody El Segundo mine in McKinley County, NM at the edge of Navajo Nation (i.e., intervention mine). The remaining less than 350 miners will be recruited from the Peabody Caballo and Rawhide mines at Campbell County, WY (i.e., control mine). Both surface coal mines, operated by the same company, have similar engineering, administrative and personal protective measures in place, including SARS-CoV-2 symptom & fever screening. While there will be frequent point-of-care molecular testing at the intervention site, seroprevalence (baseline, 3, 6, and 12 m) will be measured as an outcome at both sites.

6. Study Timelines

The duration of individual subject’s participation in this research is estimated to be approximately 12 months from the time they give and sign informed consent. We anticipate that all study participants will be enrolled in the first month of the recruitment and enrollment. Below are milestones with estimated dates of completion. The dates may be adjusted as necessary depending on the completion of previous milestones.

Milestone 1: Completion of planning, contracts, purchase of tests and supplies, protocols and IRB approval: by January 2021.

Milestone 2: Recruitment and collection of data: January 2021 through March 2022 (anticipated).

Milestone 3: Data analysis and dissemination: July 2021 through November 2022 (anticipated).

7. Study Endpoints:

7.1. Specific Aim 1:

Predictor and Outcome variables: Screening test acceptance by miners is measured for each eligible work shift and cumulative acceptance rate (i.e., outcome) is calculated over the study timeframe (frequency of tests /number of eligible shifts worked, max=less than 60). Characteristics predicting acceptance include self-reported educational and racial/ethnic minority status (from baseline questionnaire), self-reported prior SARS-CoV-2 infection or vaccination (from app), evidence of prior infection (from a prior positive screening test), and daily county incidence and prevalence infection rates (from publicly available data). Focus group discussions and/or individual interviews will be performed in a sample of subjects at the intervention mine (in NM) to better understand ‘testing hesitancy’ towards the end of the study, using an interview script and trained interviewers. Only approved study members will be performing interviews.

Expected outcomes: We anticipate a higher testing acceptance rate among non-Hispanic whites and those with higher self-reported educational status. Conversely, we expect lower acceptance rates among those with prior infection (or vaccination), and during time

PROTOCOL TITLE: Keeping rural minority ‘essential’ workplaces open safely during the COVID-19 pandemic: The role of frequent point-of-care molecular workplace surveillance for miners

intervals in which incidence of infection in the County is either trending down or at a low level.

7.2. Specific Aim 2:

Predictor and Outcome variables: Predictor variable is the sensitivity of the screening test in our study conditions. Outcomes are a) the sensitivity of the screening test reported by others in controlled settings, and b) viral load measurements in upper respiratory specimens (i.e., repeat nasal and NP swab).

Expected outcomes: We anticipate that the screening test results can be confirmed by detecting the SARS-CoV-2 load, within the limit of RT-qPCR detection. Based on our preliminary data (Fig. 2), our detection limit is ≥ 100 viral copies per mL (32). This level of detection is contingent on obtaining enough sample material. It remains unclear if a self-collected nasal swab collected in a real-world setting will consistently yield enough sample material to detect SARS-CoV-2. Since we will incorporate a primer and probe for the detection of the human ribonuclease P gene in our assay, we can directly determine if there is sufficient sample material on the screening test for the detection of SARS-CoV-2. The study design will also allow us to determine if the level of the virus on the nasal swab, self-collected in a real-world setting, is comparable in its ability to detect SARS-CoV-2 as that of a health personnel-collected NP swab.

7.3. Specific Aim 3:

Predictor and Outcome variables: The predictor variable is the mine status (intervention vs. control). The primary outcome is any *new* seropositivity for SARS-CoV-2 IgM or IgG at 3, 6, or approximately 12 months relative to baseline. The serologic test (depending upon availability, finalized using NIH recommendation) allows for the qualitative detection of IgG or IgM antibodies (separately) against SARS-CoV-2, indicating recent (IgM: 3-5 days) or prior infection (currently unknown). We will also study the presence of symptoms or fever, irrespective of infection status, as an alternative study outcome for hypothesis 3A. Costs of the test-based surveillance program, employee absenteeism patterns, and mine coal production will contribute towards defining the outcome variables for hypothesis 3B. At a minimum, a valuable outcome is to determine surveillance program costs, which have not been previously established for this rural industry setting, organization size, or proposed surveillance frequency. Additionally, variance in outcome measures—defined as employee days lost due to incident infection, mine productivity, and reduction in worksite infection rate—across the two sites will be used to estimate the cost-effectiveness of the intervention. Database management and timeline are similar to that for Aim 1.

Expected outcomes: We anticipate that as compared to the control mine, the intervention mine demonstrates lower incident seropositivity, and that workplace surveillance is cost-effective **over twelve months**.

7.4. Specific Aim 4:

Predictor, and outcome variables: The outcome variable for hypothesis 4A of incident seropositivity, is defined as in Aim 3. Predictor variables include frequency of cloth face-covering use outside the mine, occupational dust exposure intensity, presence of lung

PROTOCOL TITLE: Keeping rural minority ‘essential’ workplaces open safely during the COVID-19 pandemic: The role of frequent point-of-care molecular workplace surveillance for miners

disease (historically or measured by sputum inflammation), and race/ethnicity status. Additional predictor variables for hypothesis 4B are specific barriers and facilitators. Additional outcomes for hypothesis 4B are test and vaccine uptake.

Expected outcomes: We anticipate that low levels of use of cloth face-coverings in public settings outside the mine, high levels of occupational dust exposure intensity, baseline dust-related lung disease, and racial/ethnic minorities are each associated with a greater relative risk for incident seropositivity than those without these characteristics. We anticipate that additional predictor variables, as outlined in the previous paragraph, affect test and vaccine uptake.

8. Research Setting

Recruitment, enrollment, and data collection will be conducted at the Peabody El Segundo mine in McKinley County, NM (i.e., intervention mine) and the Peabody Caballo and Rawhide mines at Campbell County, WY (i.e., control mine). Both surface coal mines, operated by the same company, have similar engineering, administrative and personal protective measures in place, including SARS-CoV-2 symptom & fever screening.

Baseline survey will be collected from both intervention and control mine sites but the additional questionnaire (and sputum collection) will be limited to the NM mine site only.

Confirmatory diagnostic tests, which are standard of care RT-PCR tests, will be conducted at TriCore Reference Laboratories from samples collected at the Peabody El Segundo mine or at the Cibola General Hospital (where TriCore Reference Laboratories currently provide reference laboratory services). The results from the standard of care test will be provided by TriCore to the study investigators. This does not require a data user agreement.

Since the confirmatory diagnostic standard of care test is qualitative, we will also quantify viral load (\log_{10} copies/mL) from nasal (self-collected) and NP (collected by healthcare personnel) swab specimens using research diagnostic RT-qPCR tests established in the research laboratory of [name] at the Center of Global Health in the University of New Mexico’s Department of Internal Medicine. The specimens for the research diagnostic tests will be collected at the Peabody El Segundo mine or at the Cibola General Hospital. Any specimens collected will be transferred to the [name] laboratory using a Materials Transfer Agreement (MTA)

Statistical analysis will be completed at the University of New Mexico Health Sciences Center.

We will engage and work with the Mining Advisory Council, chaired by a partner, [name]. This council allows stakeholders to review research materials and protocols.

9. Resources Available

This study is based on the collective experience, expertise and infrastructure put together by a respected team of researchers, and community and clinical experts from the University of New Mexico and the Peabody mine sites in the states of New Mexico and Wyoming. This collaborative team, from the University of New Mexico (UNM) Health Sciences Center (HSC), Miners Colfax Medical Center, the Peabody El Segundo Mine, and the Peabody Caballo and Rawhide Mine, combine expertise in miner epidemiology, infectious disease, clinical care, and community-based prevention and care. The team at UNM will include Dr.

PROTOCOL TITLE: Keeping rural minority ‘essential’ workplaces open safely during the COVID-19 pandemic: The role of frequent point-of-care molecular workplace surveillance for miners

[name] (PI), [name] (Co-I), [name] (Co-I), [name] (Co-I), [name] (Co-I), [name] PhD, (Co-I), [name] (Co-I), [name] (Co-I), and [name] PhD, (Co-I).

10. Prior Approvals

UNM HSC IRB approval will be obtained before beginning any study activities.

11. Multi-Site Research

This is a single site study (i.e., at UNM HSC), with recruitment at two mine sites. This does not qualify as multi-site search. This study will take place and recruit participants at the (1) Peabody El Segundo Mine in McKinley County, NM at the edge of Navajo Nation (i.e., intervention mine), and the (2) Peabody Caballo and Rawhide mines at Campbell County, WY (i.e., control mine). Laboratory diagnostic testing will be conducted at TriCore Reference Laboratories. Since the diagnostic test is qualitative, we will also quantify viral load (\log_{10} copies/mL) from nasal (self-collected) and NP (collected by healthcare personnel) swab specimens using RT-qPCR established in the research laboratory of [name] at the Center of Global Health in the University of New Mexico’s Department of Internal Medicine. Data storage and analysis will be conducted at the University of New Mexico Health Sciences Center. The PI will have regular communication with the locations to confirm all research staff are competent, properly trained; they will have the most current version of the protocol, consent documents, and HIPAA authorization; any modifications will be communicated to sites and implemented only after IRB approval; they will safeguard all research data; any non-compliance with the study protocol or applicable requirements will be reported immediately to the PI; all adverse events, interim results and study closure determinations will be communicated via email and/or teleconference between the PI and study staff.

12. Study Procedures

During the baseline study visit, former miners and never-miners will complete a comprehensive baseline survey. Additional study procedures are outlined below

Overview of study procedures		
Measurement	Intervention mine, NM, n=less than 250	Control mine, WY, n=less than 350
Baseline survey: Demographics (age or DOB, gender or sex, race and ethnicity, education, household income, insurance, height, weight, Mailing residential address and if PO Box, physical mailing address, phone number, medical history including hypertension, diabetes, COPD, asthma, pneumoconiosis, immunocompromised state, cardiovascular disease, smoking, environmental tobacco smoke exposure, home access to running water, use of household wood or coal smoke, d tobacco, , current medications, history of prior COVID hospitalization, shared transportation	At the time of study enrollment, using paper and/or REDCap	
Additional questionnaire: Demographics (age or DOB, gender or sex, race and ethnicity, education, household income, insurance, Mailing residential address and if PO Box, physical mailing address, phone number, medical history, smoking, history of prior COVID hospitalization, Testing and vaccination history	Once between 6 and 12 months, using paper, or electronic (e.g. REDCap)	None

PROTOCOL TITLE: Keeping rural minority ‘essential’ workplaces open safely during the COVID-19 pandemic: The role of frequent point-of-care molecular workplace surveillance for miners

Web-based phone app questionnaire: Symptoms; frequency of cloth face-covering use outside the mine ; vaccination history, infected contacts, & history of prior COVID infection	Each work shift via the phone app	
Measured fever screen	Each work shift measure, recorded via REDCap (normal vs. abnormal)	
Nasal swab (self-collected) screening test	Alternate shift collection plus test acceptance data entered into REDCap	None
Nasopharyngeal swab (trained professional or TP-collected) diagnostic test (RT-PCR, TriCore labs)	All abnormal screening tests (collected at TriCore Cibola) & sample (n=approximately 200) of normal screening tests (collected at mine site) plus test acceptance data entered into REDCap	None prescribed
Nasal (self-collected) and nasopharyngeal swab (TP-collected) research test (RT-qPCR, [name] labs)	All abnormal & sample of normal tests as above	None prescribed
Serology	Blood sample at baseline, 3, 6, and approximately 12 months plus test acceptance data entered into REDCap	
Occupational dust exposure intensity	Every work shift via job-exposure matrix created by occupational safety team via REDCap	
Daily county incidence and prevalence data	Recorded daily by study coordinator from public health records entered into REDCap	
Focus group discussions and/or individual interviews to study “testing hesitancy”	Yes	No
Spontaneous home collected sputum sample	Yes once at approximately 12 months	No

12.1. Specific Aim 1:

Miners work one of two twelve-hour shifts daily, in repeated patterns of 4 days on followed by 4 days off work. At the beginning of each alternate work shift, each miner, irrespective of symptom status, will provide supervised self-collected midnasal swabs to trained mine safety personnel at the mine entrance. The safety personnel will run the screening test on swabs at the mine site. Miners with a positive screening test will undergo a confirmatory diagnostic test, and will be: 1) referred to their healthcare provider; 2) offered telemedicine evaluation at UNM, for those interested, and 3) removed from the workplace per CDC guidance (28). The final assay for the screening test will be decided based on advice from the NIH RADx-UP Coordinating and Data Collection Center. Acceptance data will be entered at the mine site by the safety personnel into a Research Electronic Data Capture (REDCap) database. Focus group discussions and/or individual interviews will be performed in a sample of subjects at the intervention mine in NM to better understand ‘testing hesitancy’ towards the end of the study.

12.2. Specific Aim 2:

Miners with any positive screening test (plus a sample of ~200 miners with a negative test) will undergo trained professional collected NP swab (for RT-PCR diagnostic testing), self-collected nasal swab (for RT-qPCR) and trained professional collected NP swab (for RT-qPCR). Database management and timelines will be similar to those described in Aim 1.

12.3. Specific Aim 3:

PROTOCOL TITLE: Keeping rural minority ‘essential’ workplaces open safely during the COVID-19 pandemic: The role of frequent point-of-care molecular workplace surveillance for miners

In brief, at the beginning of each work shift, trained mine safety personnel will obtain the following: 1) 24-hour history of SARS-CoV-2 symptoms, provider diagnosis of infection, close contact with any infected, vaccination, and use of cloth face-covering in public settings outside the mine, using a web-based phone app, also available using a computer connected to the Internet; and 2) body temperature measurement using a no-touch forehead infrared thermometer. The web-based phone app, created by Ingenuity Software Inc., will be accessed by the subjects with password protection. The information will be encrypted during data transfer to a secure server that resides at the UNM HSC and will auto-populate the REDCap database. The phone app has been approved by UNM HSC IT.

At the beginning of each alternate shift, the mine safety team will collect a supervised self-collected nasal swab from each worker for point-of-care screening testing, as described in Aim 1. Fingerstick or venipuncture blood samples will be obtained at the mine site from all study participants at the time of enrollment, and at 3, 6, and approximately 12 months (no more than 24 ml or 4.9 teaspoons each visit) to determine seropositivity, using the COVID-19 IgG/IgM antibody test. Employee absenteeism (both general and screen test results-driven) and coal production records will be analyzed.

12.4. Specific Aim 4:

Predictor variables are listed in Table titled Overview of Study Procedures. Database management and timeline will be similar to that for Aim 1.

13. Data Analysis

13.1. Specific Aim 1:

Predictor and Outcome variables: Test acceptance by miners is measured for each eligible work shift and cumulative acceptance rate (i.e., outcome) is calculated over the study timeframe (frequency of tests /number of eligible shifts worked, max number estimated at less than 120). Characteristics predicting acceptance include self-reported educational and racial/ethnic minority status (from baseline questionnaire), self-reported prior SARS-CoV-2 infection or vaccination (from app), evidence of prior infection (from a prior positive screening test), and daily county incidence and prevalence infection rates (from publicly available data).

Statistical approach: Cumulative acceptance rate will be compared between groups, defined by predictive characteristics. Poisson regression with indicator variables will be used to assess the effects of miner characteristics on cumulative acceptance rates. Analyses will use the number of shifts in which tests were available to miners for the rate denominator (offset) to account for absenteeism. Longitudinal analysis of shift-level acceptance by miners will be examined using mixed model regression for binary outcomes that account for repeated measures. Within-miner factors will include time-varying SARS-2-COV-2 exposure (personal and community) and vaccination status, and linear and nonlinear time trends.

PROTOCOL TITLE: Keeping rural minority ‘essential’ workplaces open safely during the COVID-19 pandemic: The role of frequent point-of-care molecular workplace surveillance for miners

Power calculations: If we recruit less than 250 miners, we have the power to estimate 85% acceptance rate \pm 4.6%. For a comparison of acceptance rates between predictor groups, we assume, for example, non-Hispanic white and minority miners (1/3 and 2/3 of the study population respectively) have 85% and 80% acceptance respectively. We used simulation to assess power for Poisson regression analyses where the rate denominator (offset) is the number of miner workdays, assumed to be 95% of possible days. For these conditions, power is 94% for a 5% lower acceptance rate for minority miners. We also used simulation to assess the planned longitudinal analysis of miner acceptance by assuming that miners attended work 95% of the shifts, that initial acceptance is 85% and that there is a linear decline in acceptance over the study to a final acceptance rate of 80%. For repeated measures on about 200 miners, the power to detect a linear decrease to 80% is 95%.

13.2. Specific Aim 2:

Statistical analysis: We will compare screening test performance measures between our real-world study setting and controlled settings (as published by others). We will use a one-sample Exact test for a binomial proportion to test whether sensitivity for the screening test is the same as that published. We will correlate screening test results with quantitative viral loads, and perform Bland-Altman plots to reveal systematic differences between viral loads collected by the two sampling methods.

Power Calculations: If we conservatively estimate identifying 25 true positive miners, using a one-sample Exact test for a Binomial proportion equal to the comparison test, we have the power (>90%) to detect a difference between the screening and the comparison test if the screening test sensitivity is 90% or lower.

13.3. Specific Aim 3:

